16.2 Method of Detecting AEs and SAEs

At each study visit, care should be taken not to introduce bias when detecting AEs and/or SAEs. Open-ended and non-leading verbal questioning of the subject is the preferred method to inquire about AE occurrence. Appropriate questions include:

- “How are you feeling?” **or** “How does your child seem to feel?”
- “Have you had any (other) medical problems since your last visit/contact?” **or** “Has your child had any (other) medical problems or seem to act differently in any way since his/her last visit/contact?”
- “Have you taken any new medicines, other than those provided in this study, since your last visit/contact?” **or** “Has your child needed to take any medicines, other than those provided in this study, since his/her last visit/contact?”

16.3 AE and SAE evaluation**I. Assessment of Severity (i.e. intensity)**

The Investigator will make an assessment of intensity for each AE and SAE reported during the study and will assign it to one of the following categories:

- **Mild:** an event that is easily tolerated by the subject, causing minimal discomfort and not interfering with everyday activities.
- **Moderate:** an event that is sufficiently discomforting to interfere with normal everyday activities.
- **Severe:** an event that prevents normal everyday activities.

An AE that is assessed as severe will not be confused with an SAE. Severity is a category utilized for rating the intensity of an event; and both AEs and SAEs can be assessed as severe. An event is defined as ‘serious’ when it meets at least one of the pre-defined outcomes as described in the definition of an SAE.

II. Assessment of Seriousness

When an AE/AR occurs the Investigator responsible for the care of the patient must first assess whether the event is serious using the definition given in **Table 8**. If the event is serious, then an SAE form must be completed and the SC notified.

III. Assessment of Causality

The Investigator must assess the causality of all events/reactions in relation to the trial therapy using the definitions in **Table 9**.

There are 5 categories: unrelated, unlikely, possible, probable and definitely related. The causality assessment is unrelated or unlikely to be related the event is classified as an AE. If the causality is assessed as either possible, probable or definitely related then the event is classified as a AR. If a drug is possibly related to an AE, this should be noted on the follow up form.

Table 9. Causality Assessment

Relationship	Description	Type
Unrelated	There is no evidence of any causal relationship	AE
Unlikely	There is little evidence to suggest there is a causal relationship (e.g., the event did not occur within a reasonable time after administration of the trial medication). There is another reasonable explanation for the event (e.g., the patient’s clinical condition, other concomitant treatment).	AE

Possible	There is some evidence to suggest there is a causal relationship (e.g., because the event occurs within a reasonable time after administration of the trial medication). However, the influence of other factors may have contributed to the event (e.g., the patient's clinical condition, other concomitant treatment).	AR
Probable	There is evidence to suggest there is a causal relationship and the influence of other factors is unlikely.	AR
Definitely related	There is clear evidence to suggest there is a causal relationship and other possible contributing factors can be ruled out.	AR

IV. Assessment of Expectedness

If the event is a SAR the Investigator must assess the expectedness of the event. If a SAR is assessed as being unexpected it becomes a SUSAR. The definition of an unexpected adverse reaction (UAR) is given in **Table 8** and is one not previously reported in the current SmPC (for the authorized product, namely deferasirox) or IB (for the IMP, deferiprone).

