16. ADVERSE EVENTS (AE) AND SERIOUS ADVERSE EVENTS (SAE) REPORTING

According to ICH E6 Guideline (Good Clinical Practice, GCP), both Investigators and Sponsor follow specific procedures when notifying and reporting adverse events/reactions in clinical trials.

The Principal Investigator or qualified site staff is responsible for detecting, documenting and reporting events that meet the definition of an AE or SAE.

AEs will be collected from the start of Investigational Product and until the follow-up contact. Medical occurrences that begin prior to the start of investigational product but after obtaining informed consent should be recorded separately from the Medical History/Current Medical Conditions CRF.

SAEs will be collected over the same time period as stated above for AEs. However, any SAEs assessed as related to study participation (e.g. investigational product, protocol-mandated procedures, invasive tests, or change in existing therapy) will be recorded from the time a subject consents to participate in the study up to 30 days from last dose or study related invasive procedure. All SAEs will be recorded and reported to Safety Contact (SC) within 24 hours after the Investigator has become aware of the event, as indicated in Section 16.3.

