16.1 Definitions

In this trial protocol the definitions reported in **Table 8** apply according to the Art.2 of the Directive 2001/20/EC.

Table 8. Definitions

TERM	DEFINITION
‘Adverse Event’ (AE)	any untoward medical occurrence in a patient or clinical trial subject administered a medicinal product and which does not necessarily have a causal relationship with this treatment ^A
‘Adverse Reaction’ (AR)	all untoward and unintended responses to an investigational medicinal product related to any dose administered
‘Serious Adverse Event or Serious Adverse Reaction’ (SAE or SAR)	any untoward medical occurrence or effect that at any dose: 
 ▪ results in death ▪ is life-threatening^B ▪ requires hospitalisation or prolongation of existing hospitalization^C ▪ results in persistent or significant disability or incapacity^D ▪ is a congenital anomaly or birth defect ▪ other medically important/clinically significant events^E
‘Unexpected Adverse Reaction’ (UAR)	an adverse reaction, the nature or severity of which is not consistent with the applicable product information (e.g. Investigator's brochure for an unauthorised investigational product or summary of product characteristics for an authorised product)

^AAn AE can therefore be any unfavourable and unintended sign (including an abnormal laboratory finding), symptom, or disease (new or exacerbated) temporally associated with the use of a medicinal product.

^BThe term 'life-threatening' in the definition of 'serious' refers to an event in which the subject was at risk of death at the time of the event. It does not refer to an event, which hypothetically might have caused death, if it were more severe.

^c In general, hospitalization signifies that the subject has been detained (usually involving at least an overnight stay) at the hospital or emergency ward for observation and/or treatment that would not have been appropriate in the physician's office or outpatient setting. Complications that occur during hospitalization are AEs. If a complication prolongs hospitalization or fulfils any other serious criteria, the event is serious. When in doubt as to whether "hospitalization" occurred or was necessary, the AE should be considered serious.

Hospitalization for elective treatment of a pre-existing condition that did not worsen from baseline is not considered an AE.

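### Section 16.3 IV restates the test for an unexpected reaction without Table 8's severity criterion, so the same serious reaction can be classed as a SUSAR or not depending on which half of the sentence is followed

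*Combined protocol and SAP*

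**What the plan says.** **Expectedness.** Section 16.1 states that the Table 8 definitions apply in this protocol. Table 8 defines an unexpected adverse reaction as "an adverse reaction, the nature or severity of which is not consistent with the applicable product information". Section 16.3 IV gives the expectedness judgement to the investigator and attaches a consequence: "If a SAR is assessed as being unexpected it becomes a SUSAR". It then says "The definition of an unexpected adverse reaction (UAR) is given in" Table 8, and continues that such a reaction "is one not previously reported in the current SmPC (for the authorized product, namely deferasirox) or IB (for the IMP, deferiprone".

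**Relatedness.** The opening of Section 16 collects AEs, and SAEs with them, from the start of investigational product to the follow-up contact. It extends collection back to consent for "any SAEs assessed as related to study participation (e.g. investigational product, protocol-mandated procedures, invasive tests, or change in existing therapy". Section 16.3 III sets the grading rule: "The Investigator must assess the causality of all events/reactions in relation to the trial therapy", using the five categories of Table 9. Table 9's timing examples refer to trial medication. For instance, one reason for rating an event unlikely to be related is that "the event did not occur within a reasonable time after administration of the trial medication".

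**Reporting.** Under 16.3 II, seriousness alone triggers the SAE form and notification of the Safety Contact. Section 16 and Section 16.4 require all SAEs to reach the Safety Contact within 24 hours, and 16.4 has the sponsor review every SAE report. None of these rules depends on expectedness.

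**The concern.** One sentence in 16.3 IV contains two tests for the same classification. Table 8's test has two limbs, nature and severity. The restatement asks only whether the reaction has been reported before in the reference document. The restatement also names the reference document for each drug, so it is the part a site is likely to use when completing the form.

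The SUSAR label is at stake. Section 16.3 IV makes it depend on the investigator's expectedness call, in a trial that enrols children from 1 month of age and uses a new strength of the deferiprone solution. Two sites could classify the same event differently, and each could point to the protocol in support.

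The relatedness wording has a similar mismatch. An SAE before first dose enters SAE collection only if it is judged related to study participation, but the one grading scale in the protocol asks about trial therapy, which has not yet been given.

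**Working it through.** No calculation applies and the plan states no figure to reproduce. The check sets the provisions side by side.

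**1. Expectedness: the two tests case by case**

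- Serious reaction of a type absent from the SmPC or IB. Table 8: unexpected, by nature. Restatement: unexpected. The tests agree.
- Serious reaction of a listed type, with severity consistent with the listing. Table 8: expected. Restatement: expected. The tests agree.
- Serious reaction of a listed type, with severity beyond the listing. Table 8: unexpected, by severity. Restatement: already reported, so expected. The tests conflict.

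The disagreement is confined to the third case. Section 3.1 supplies an illustration: renal impairment was identified as a deferasirox risk after marketing, and the SmPC was updated. A serious renal reaction worse than the SmPC describes would fall in the third case. What severity the SmPC lists is not in the text available here (Annex 1 appears by title only), so this shows the mechanism and does not establish a particular misclassification.

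**2. What happens to a third-case event**

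- It is serious, so the SAE form is completed and the Safety Contact notified (16.3 II).
- It reaches the Safety Contact within 24 hours (Sections 16 and 16.4).
- The sponsor reviews it and follows country-specific regulatory reporting requirements (16.4).
- What may be missing is the SUSAR label. Section 16.4 bars the sponsor from overruling the investigator's causality assessment. It neither bars nor requires a sponsor reassessment of expectedness.

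**3. Relatedness: SAEs by timing and cause**

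- From first dose to the follow-up contact, any cause, procedures included: inside the ordinary SAE window.
- After consent and before first dose, unrelated to participation: outside SAE collection by the plan's own rule. The event is recorded separately as a medical occurrence (Section 16) and appears as a medical event at the Day 0 visit (Section 7.2.1).
- After consent and before first dose, related to participation: inside SAE collection under Section 16, if the investigator makes that judgement. Neither 16.3 III nor Table 9 provides a category for it.

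Only the third group is affected. Consent is taken at Visit 1, between day -28 and day -8, so for a patient already on a chelator the interval to Day 0 is 8 to 28 days. It includes the six washout days (day -6 to day -1). Chelation-naive patients have no washout and are not held to the same run-in timing. Baseline MRI may be done up to 20 days before Day 0, so protocol procedures can also fall in this interval.

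**The case against.** The strongest reply on expectedness is that Table 8 governs. Section 16.1 adopts its definitions for the protocol, and the sentence in 16.3 IV names Table 8 before it paraphrases. On that view the paraphrase serves mainly to identify the SmPC for one drug and the IB for the other. This has force: the text does not replace Table 8, and one cannot say that every worse-than-listed reaction would be reclassified as expected. It does not remove the conflict, because the paraphrase still states a different test in the place where the classification is made.

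A reader might go further and infer that worse-than-listed reactions escape reporting. The documents do not support that. The SAE route is independent of expectedness, and the sponsor sees each report. Section 16.6 additionally sends every confirmed neutropenia through SAE notification regardless of severity or seriousness.

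On relatedness, the reply is that Table 9 answers a different question. It separates an adverse event from an adverse reaction, and Table 8 defines an adverse reaction as a response to an investigational product, so a trial-therapy scale is the right one for that purpose. Section 16 sets its own participation test and does not route it through Table 9. An investigator can therefore rate an event unrelated to trial medication and still judge it related to participation. This stands, and it defeats the inference that the from-consent rule can never operate or that such events are lost. What remains is that the protocol describes no place to record the second judgement.

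**Conclusion.** The expectedness point holds as an internal conflict between Section 16.3 IV and Table 8. It affects one class of event, serious reactions of a listed type and greater-than-listed severity, and its consequence is a possible missing SUSAR label on a report the sponsor already holds. The documents give no event counts, so no frequency can be attached. The conclusion assumes that some investigators will apply the restatement and not return to Table 8, and that the sponsor does not routinely reassess expectedness, on which the plan is silent.

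The relatedness point is secondary: a missing cross-reference and recording item for participation-related SAEs between consent and first dose. It rests on the protocol text alone. The SAE section of the e-CRF, the Study Procedures Manual and the safety reporting flowchart (Figure 3) could not be checked, and any of them may already contain such an item.

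Neither point touches the endpoints, the sample size or the analysis. Both are worth correcting because they concern how serious harms are classified and the correction is small.

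**What to change.** **Section 16.3 IV.** Keep the reference to Table 8. Replace the restatement with Table 8's own criterion, so that a reaction is unexpected when its nature or its severity is inconsistent with the named document: the current SmPC for deferasirox, the IB for deferiprone. The cost is one sentence, and slightly more reactions will be handled as unexpected.

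**Section 16.3 III.** Add a cross-reference to the participation-relatedness rule in Section 16. Unless the SAE form already has one, add a yes/no item asking whether the event is related to a study procedure, the washout or a change in existing therapy. Keep Table 9 for relatedness to trial therapy, and let a yes on the new item bring an SAE that occurs before first dose into the from-consent collection. The cost is one cross-reference and one form field.

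Check Figure 3 against both changes so that the flowchart and text agree.

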16.4 Reporting

Investigator Responsibility

All SAEs must be reported by the Investigator to SC on a SAE form within 24 hours of the investigator being aware of the event.

Notification procedure:

[figure not shown]
- I. The SAE form must be completed by the Investigator or by trained authorised person with the right to access in the e-CRF. The responsible investigator or the trained authorised person should complete the online "SAE section" of the e-CRF, print it in a pdf format and then fax it to the Safety Contact as soon as possible. The initial report shall be followed by detailed reports as appropriate. Even if the Investigator has minimal information to include in the initial report it is important that he should always make an assessment of causality for every event prior to the initial transmission of the SAE data. The Investigator may change his/her opinion of causality in light of follow-up information and then sending the SAE form as follow up, amending the SAE data collection system accordingly.
- II. Send the SAE form by fax to the SC.
- III. Follow-up: patients must be followed-up until clinical recovery is complete and laboratory results have returned to normal baseline, or until the event has stabilised. Follow-up should continue after completion of protocol treatment if necessary. Follow-up information should be noted on a further SAE form in the "SAE section" of the e-CRF, by adding a Follow up form to the Initial Form. The Follow up form shall be printed in pdf format and sent by fax to the Safety Contact as information become available. Extra annotated information/or copies of test results may be provided separately. The patient must be identified by trial number and date of birth only. The patient's name should not be used on any correspondence.

Sponsor Responsibility

The Sponsor will review all SAE reports received. The causality assessment given by the local Investigator at the hospital cannot be overruled and in the case of disagreement, both opinions will be provided in any subsequent reports. The Sponsor will comply with country specific regulatory requirements relating to safety reporting to regulatory authorities, IRBs/IEC/REB and Investigators. The Sponsor will also assure all Investigators are informed of any safety issues that arise during the course of the trial.

The modality by which adverse experience data are communicated by the Sponsor to study drug MAH or producer (as appropriate) are defined in an *ad hoc* agreement.

Figure 3. Safety reporting flowchart

The telephone and fax numbers of the SC are listed in the Investigator folder provided to each site.

16.5 Instructions for rapid notification of pregnancies

Each pregnancy, occurring in a participating female patient or partner of participating male patient that started during the study must be reported by the Investigator to the Sponsor within 24 hours of learning of its occurrence. Pregnancies and pregnancy follow-up as well as any SAE experienced during pregnancy

CONFIDENTIAL

DEEP Consortium
DEEP2-Efficacy/Safety Study Protocol Protocol No. DEEP-2

must be reported on the SAE Report Form. Pregnancy follow-up should describe the outcome of the pregnancy, including any voluntary or spontaneous termination, details of the birth, the presence or absence of any congenital abnormalities, birth defects, maternal or new born complications and their relation to the Sponsor study drug (or therapy).

16.6 Instructions for rapid notification of Neutropenia

In this protocol all neutropenia, defined as ANC < 1500/mm³ (confirmed in two consecutive measurements), irrespective of their severity or seriousness, will follow the procedure for SAE notification and must be reported by the Investigator to the Sponsor within 24 hours of learning of their occurrence according to the procedure described in Section 16.4 Reporting.

17. DATA SAFETY MONITORING COMMITTEE (DSMC)

The study will be conducted under the supervision of an independent DSMC. All DSMC members have extensive experience in either paediatric clinical trials and/or management of haemoglobinopathies. The DSMC is responsible for the ongoing review of a clinical trial and for making recommendations concerning the continuation, modification, and termination of the trial. Details of the DSMC membership, meeting schedule, and data review and analysis will be documented in the DSMC Charter.

18. HUMAN SUBJECTS

18.1 Institutional Review Board (IRB)/Independent Ethics Committee (IEC) /Research Ethics Board (REB)Review

Ad hoc consent and assent form will be submitted to patients and their legal representatives before enrolling in the study. These forms have been developed in the context of the DEEP Project and have been submitted to the revision of the DEEP IEC according to the current National and European ethic rules also taking in to account the Convention on Human Rights and Biomedicine (Oviedo, 4.IV.1997), its Additional Protocol concerning Biomedical Research (Strasbourg 25.I.2005). Three different assent forms have been developed taking into account different age groups that include children <6 years, 6 - 10 years and >10 years.

A signed and dated statement that the protocol and the informed consent forms have been approved by the IRB/IEC/REB must be given to the Sponsor before study initiation.

Disclosure and Confidentiality

Study procedures are compliant with the Convention for the Protection of Individuals with regard to Automatic Processing of Personal Data (Strasbourg, 28.I.1981). All laboratory specimens, evaluation forms, reports, video recordings, and other records that leave the site will be identified only by the patient sequential number to maintain subject confidentiality. All records and study documents provided by the Sponsor (protocols, investigators' brochures, CRFs and other material) will be kept in a locked file cabinet. All computer entry and networking programs will be done using patient sequential number only. Clinical information will not be released without written permission of the subject, except as necessary for monitoring by IRB, the EC, the sponsor, or the sponsor's designee.

CONFIDENTIAL

DEEP Consortium
DEEP2-Efficacy/Safety Study Protocol

Protocol No. DEEP-2

By signing the protocol, the investigator agrees to keep all information provided by the Sponsor in strict confidence and to request similar confidentiality from his/her staff and the IRB. The information provided by the Sponsor to the investigator may not be disclosed to others without direct written authorization from the Sponsor, except to the extent necessary to obtain informed consent from patients who wish to participate in the trial.

18.2 Study Modification/Discontinuation

Any change or addition to this protocol requires a written protocol amendment that must be approved by the Sponsor and the Trial Coordinating Investigator before implementation. Amendments significantly affecting the safety of subjects, the scope of the investigation or the scientific quality of the study, require additional approval by the IRB/IEC/REB of all centres, and, in some countries, by the regulatory authority. Examples of amendments requiring such approval are:

1. an increase in drug dosage or duration of exposure of subjects
2. a significant change in the study design (e.g. addition or deletion of a control group)
3. an increase in the number of invasive procedures to which subjects are exposed
4. an addition or deletion of a test procedure for safety monitoring.

These requirements for approval should in no way prevent any immediate action from being taken by the investigator or by the Sponsor in the interests of preserving the safety of all subjects included in the trial. If an immediate change to the protocol is felt to be necessary by the investigator and is implemented by him/her for safety reasons the Sponsor should be notified and the IRB/IEC/REB at the centre should be informed within 10 working days.

Amendments affecting only administrative aspects of the study do not require formal protocol amendments or IRB/IEC/REB approval but the IRB/IEC/REB of each centre must be kept informed of such administrative changes. Examples of administrative changes not requiring formal protocol amendments and IRB/IEC/REB approval that can be treated as administrative amendments include:

1. changes in the staff used to monitor trials
2. minor changes in the packaging or labelling of study drug.

